Recent advances in the understanding of the etiology of obesity, along with development of novel pharmaceutical and surgical treatment options have yet to contribute to a reduction in the obesity prevalence in the US population. Improving diet and physical activity are still the foundation of current obesity treatments. One approach shown to be useful in modulating energy intake to support weight loss in overweight/obese individuals is provision of pre-portioned foods and beverages (i.e., meal replacements; Cheskin 2008, Hannum 2004 and 2006, 1-Ieymsfield 2003). Indeed, a group of obesity experts has considered the evidence behind this strategy as sufficiently strong and consistent to be considered empirically proven compared to more conventional dietary advice, such as food choices based on general concepts like balance, variety, and moderation (Casazza 2013). Some commercially available weight loss programs utilize this approach; however, data from randomized clinical trials documenting the degree of weight loss achievable with these programs is often lacking.

In this context, the role of commercially-available weight loss programs has received increased attention by the scientific community (Gudzune 2015, Jensen 2014). In 2013, joint guidelines issued by the American Heart Association, the American College of Cardiology and The Obesity Society for the management of overweight and obesity in adults (Jensen 2014) examined the use of some commercial programs. The general recommendation was that some commercially available programs that promote a comprehensive lifestyle intervention can be prescribed as an option for weight loss provided there is peer-reviewed published evidence of their safety and efficacy. Yet, well designed, randomized, controlled trials directly testing efficacy of many programs have not been conducted. Thus, a need exists to identify evidence-based, commercially available weight management programs.

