## 2.0. TRIAL DESIGN AND VISIT STRUCTURE

This randomized, controlled, 16-week parallel study includes one screening visit (Visit 1; week -1), one baseline visit (Visit 2; week 0), and five clinic visits (Visits 3,4,5,6, and 7; weeks 2, 4, 8, 12, and 16). Subjects will be randomly assigned in 1:1:1 ratio to one of the three groups (TSFL Program Group, MEDD Program Group, or Control Group) within which the subjects will receive the following interventions:

- **TSFL Program Group:** The TSFL Program group will be assigned to the Optimal Weight 5 & 1 Plan™ for weight loss. This is a portion-controlled, nutritionally balanced, low calorie weight loss meal plan (800-1000 kcal/day) that consists of five Medifast meal replacements, one lean and green meal, and one optional snack each day. The Medifast meal replacements are nutrient dense and fortified with 24 vitamins and minerals to ensure adequate micronutrient nutrition while on a calorie restricted meal plan. All Medifast meal replacements share a similar nutritional profile, allowing them to be used interchangeably. All Medifast meal replacements required for the meal plan will be provided to the TSFL Group participants throughout the 16-week weight loss period of the study. The lean and green meal is a self-prepared meal consisting of a specified amount of lean protein, non-starchy vegetables, and healthy fats. Participants will purchase and prepare foods used for the lean and green meals on their own. Additionally, the Medifast Flavors of Home® products offer a “heat and serve” alternative to the self-prepared lean and green meal for occasional use. TSFL participants will receive up to six Flavors of Home products per month during the study. TSFL participants will receive a list of self-selected foods (purchased by the participants) that can be used for the optional snack. In addition, participants will also be provided with up to two boxes (i.e., 14 individual packets) of Medifast snacks which can serve as a portable, pre-portioned, ready-to-eat alternate snack option.

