### **3.0. SIZE OF TRIAL POPULATION**

A standard deviation of 15.0 lb for change in body weight over 16 weeks was derived from the largest variability observed in a previous study by Davis et al. (2010) that compared weight loss over 16 weeks on the Medifast 5 & 1 Plan® (-29.8 ± 13.0 lb) vs. a food-based isocaloric control diet (-14.3 ± 15.0 lb). Using this estimate of expected variability and accounting for a more conservative mean difference in weight loss between groups over a similar timeframe, an evaluable sample of 55 participants in each group (165 total) will provide 80% power to detect a difference of 9.0 pounds (an effect size  $d$  of 0.60). This assumes a nominal  $\alpha = 0.025$  (two-sided) accounting for two primary comparisons, each Medifast group compared to the control group, in order to maintain an overall type I error of  $\alpha = 0.05$ . To account for possible attrition, a total sample of 198 participants will be randomized.

Subjects will be randomized to one of three groups (1:1:1 ratio) stratified by sex to ensure each group is allocated a maximum of 25% male participants. Additionally, the total study sample will be limited to  $\leq 10\%$  of participants with a BMI between  $\geq 27.0$  and  $< 30.0$  kg/m^2, but randomization will not be stratified by BMI.

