### **5.0. ANALYSIS POPULATIONS**

All statistical analyses will be conducted using SAS® software for Windows (version 9.4 or higher, Cary, NC).

An Intent-To-Treat (ITT) population will include all subjects who were randomized into the study. A modified ITT (mITT) population will include all randomized participants that had at least one post-baseline weight measurement. In addition, a Completers population will comprise subjects who were randomized into the study and completed all clinic visits during the entire 16-week study period.

All decisions regarding population assignment will be documented prior to database lock.

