### 9.0. STATISTICAL METHODS

Descriptive statistics (number of subjects, mean, SEM, median, interquartile limits, minimum and maximum) will be presented for quantitative variables. Ratings for categorical variables will be presented as counts and percentages. All tests of significance, unless otherwise stated, will be performed at alpha=0.05, two-sided.

Baseline comparisons for demographic characteristics between control and intervention groups will be completed with the Chi-square test, Fisher’s exact (two-tail) test, or analysis of variance (ANOVA), as appropriate.

Analysis of covariance (ANCOVA) will be used to assess differences among intervention groups in the primary and continuous secondary outcome variables at each post-randomization visit. The ANCOVA model will contain a term for intervention, with sex and baseline measures as covariates. Least squares mean values and corresponding SEM will be derived from the final ANCOVA model for each intervention group.

Counts and percentages of subjects who experience weight loss of  $\geq 5\%$  and  $\geq 10\%$  between baseline (Visit 2) and each post-randomization visit (visits 3, 4, 5, 6, and 7) will be presented. Differences among intervention groups in subjects with weight loss of  $\geq 5\%$  and  $\geq 10\%$  will be assessed using a generalized linear model with a logit link and binomial distribution specified. The model will contain a term for intervention, with sex as a covariate.

Differences among intervention groups in individual Satisfaction and Health/Well-being questionnaire scores will be assessed using a generalized linear model with a cumulative logit link and multinomial distribution specified. The model will contain a term for intervention, with sex and absolute change in weight as covariates.

For the analyses of body weight, body composition parameters, and body circumference parameters, each active group will be compared to the control group using a step-down Dunnett adjustment for multiple comparisons when a significant treatment effect is observed. Meanwhile,

no adjustments will be done on control vs. active comparisons on the remaining outcome variables.

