#### **11.0. SAFETY ANALYSIS**

Safety assessments will be determined from intervention-emergent AEs that occur after randomization at Visit 2 (week 0). Possible differences in the number of participants with at least one AE will be assessed with Chi-Square or Fisher's exact test.

Participants who achieve a BMI of  $19.0 \text{ kg/m}^2$  or below will discontinue the weight loss diet and begin a maintenance diet and will be asked to return for remaining clinic visits. These participants will be noted in the safety analysis.

Vitals (blood pressure, pulse rate) will be summarized by group with descriptive statistics.

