
Table 4.10  
Secondary Outcome Variable: Weight Loss Program Adherence Descriptive Statistics and P-values

Parameter		TSFL	MEDD
Meal Replacement^	Mean (SEM)	Mean (SEM)	Mean (SEM)
	Median	Median	Median
	Q1, Q3	Q1, Q3	Q1, Q3
	Min, Max	Min, Max	Min, Max
	Corr (p-value)+	0.xxx (x.xxx)	0.xxx (x.xxx)
Nutrition Support Contact	Mean (SEM)	Mean (SEM)	Mean (SEM)
	Median	Median	Median
	Q1, Q3	Q1, Q3	Q1, Q3
	Min, Max	Min, Max	Min, Max
Coaching Contact	Mean (SEM)	Mean (SEM)	
	Median	Median	
	Q1, Q3	Q1, Q3	
	Min, Max	Min, Max	
	Corr (p-value)+	0.xxx (x.xxx)	

^average meal replacement (per day) across the 16-weeks of the study

+spearman's rank-order correlation between the corresponding parameter and absolute change in body weight from baseline (Visit 2; week 0) to end of study (Visit 7; week 16)

Table 4.11  
Secondary Outcome Variable: Nutrition Support Contact P-values

Group	Parameter	Initial & Discretionary NS contact*		Initial NS contact or None**	p-value^
MEDD	% weight loss >= 5%	N (%)	N (%)	N (%)	x.xxx
TSFL	% weight loss >= 5%	N (%)	N (%)	N (%)	x.xxx

^p-values shown are generated from Fisher's exact test

\*at least two NS contacts for MEDD or at least one NS contact for TSFL

\*\*at most one NS contact for MEDD or none for TSFL

Table 5  
Summary of Subjects with at Least One Intervention-emergent Adverse Events

	Control	TSFL	MEDD	Intervention p-value*
Any Adverse Event	N (%)	N (%)	N (%)	x.xxx
Serious	N (%)	N (%)	N (%)	x.xxx
Severe	N (%)	N (%)	N (%)	x.xxx
Related to Study Treatment*	N (%)	N (%)	N (%)	x.xxx

\*p-values shown are generated from Chi-Square or Fisher's exact test, as appropriate

\* Probably or Definitely Related to Study Treatment.

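### Adverse events are compared by one three-arm p-value per row, with no estimate or interval for either program against Control

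*SAP*

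**What the plan says.** SAP 11.0 (Safety Analysis) and Protocol 8.2.3 plan the same comparison: "Possible differences in the number of participants with at least one AE will be assessed with Chi-Square or Fisher's exact test". The Table 5 shell in SAP 17.0 has four rows (any, serious, severe and treatment-related AE). Each row gives N (%) for Control, TSFL and MEDD and a single Intervention p-value, with the footnote "p-values shown are generated from Chi-Square or Fisher's exact test, as appropriate". It has no row for either program against Control, no risk difference and no confidence interval.

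No separate significance level is set for safety, so the general rule of SAP 9.0 applies: "All tests of significance, unless otherwise stated, will be performed at alpha=0.05, two-sided". SAP 16.0 assigns Table 5 to the mITT population, defined in SAP 5.0: "A modified ITT (mITT) population will include all randomized participants that had at least one post-baseline weight measurement". The sample size (SAP 3.0, Protocol 8.1) rests on body weight alone. Neither document gives an expected AE rate, a safety margin or a power figure for safety.

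The remaining safety output is descriptive. Vitals are summarized by group, AE discontinuations and deaths are counted in Table 1, and participants reaching the low BMI threshold are noted.

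**The concern.** SAP 1.0 and Protocol 4 define the question as each program compared with the control diet. The outcome tables that carry an intervention p-value (Tables 3, 4.1 to 4.7 and 4.8.2) follow this and add a comparison of each active arm with Control. Table 5 does not. If one of its rows were significant, the table would not test which program differs from Control. If a row were not significant, the table would not show how large an excess the data still allow.

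The second case matters because the trial was not sized for AEs. For plausible event rates, a material increase in one program could well give p > 0.05, and the planned analysis offers no interval to put beside that p-value.

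**Working it through.** **The plan's own figure.** SAP 3.0 uses SD 15.0 lb, a difference of 9.0 lb (d = 0.60), two-sided alpha 0.025 and 80% power. The normal approximation gives n = 2(2.241 + 0.842)² / 0.60² = 2 × 9.505 / 0.36 = 52.8, so 53 per group. At the stated 55, the noncentral t gives 80.7% power. The step from 55 to 66 per group implies 1 - 55/66 = 16.7% attrition, and 3 × 66 = 198. The figure reproduces, but it concerns weight only.

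**Inputs for the safety test.**
- Allocation: "Subjects will be randomly assigned in 1:1:1 ratio to one of the three groups" (SAP 2.0).
- Number: "To account for possible attrition, a total sample of 198 participants will be randomized" (SAP 3.0), so at most 66 per arm in Table 5. The 55 evaluable per arm serve as a lower case.
- Alpha: 0.05 two-sided (SAP 9.0).
- Control event rates: not in the documents, so assumed and varied.

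**Formula.** With x₁, x₂, x₃ participants with an event, n per arm and p̄ = (x₁ + x₂ + x₃)/(3n), the statistic is X² = Σ(xᵢ - np̄)² / [np̄(1 - p̄)]. The test rejects at X² ≥ 5.99 (2 df). Power is the sum of the three binomial probabilities over all rejecting outcomes, enumerated exactly.

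**Any AE, 15-point rise.** Chi-square power in %, for a rise in one program only / in both:

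| Control → program | 66 per arm | 55 per arm |
|---|---|---|
| 10% → 25% | 68.5 / 63.5 | 60.3 / 54.7 |
| 15% → 30% | 58.3 / 54.8 | 50.5 / 46.5 |
| 20% → 35% | 51.8 / 49.3 | 44.4 / 41.6 |
| 22% → 37% | 49.9 / 47.6 | 42.7 / 40.2 |
| 30% → 45% | 44.6 / 43.6 | 37.7 / 36.7 |
| 40% → 55% | 41.8 / 41.1 | 35.9 / 35.9 |
| 50% → 65% | 42.1 / 43.0 | 36.1 / 36.3 |
| 62% → 77% | 46.8 / 49.0 | 39.5 / 41.9 |
| 70% → 85% | 54.8 / 58.3 | 46.5 / 50.5 |
| 80% → 95% | 77.4 / 83.2 | 68.5 / 75.1 |

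**Severe or serious AE, fourfold rise, 66 per arm.** Power in %, one program / both, with the three-arm Fisher (Freeman-Halton) test beside the chi-square:

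| Control → program | Chi-square | Fisher |
|---|---|---|
| 1% → 4% | 19.1 / 10.5 | 12.6 / 9.3 |
| 2% → 8% | 39.3 / 27.0 | 34.1 / 30.5 |
| 2.5% → 10% | 49.5 / 36.8 | 43.3 / 40.1 |
| 3% → 12% | 58.4 / 46.5 | 51.8 / 48.8 |
| 4% → 16% | 72.7 / 64.1 | 66.9 / 65.3 |
| 5% → 20% | 83.2 / 77.4 | 79.2 / 78.3 |

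**A worked row.** Suppose 5/66 in one program and 1/66 in each other arm. Expected counts are 7/3 = 2.3 per arm, so Fisher applies: p = 0.22. Chi-square would also be non-significant: X² = 10.67 / (66 × 0.0354 × 0.9646) = 4.74, p = 0.09.

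The difference is 7.58% - 1.52% = 6.06 points. The Wilson 95% limits are 3.28% to 16.54% for 5/66 and 0.27% to 8.10% for 1/66. Newcombe's limits follow:
- lower: 6.06 - √[(7.58 - 3.28)² + (8.10 - 1.52)²] = 6.06 - 7.86 = -1.8
- upper: 6.06 + √[(16.54 - 7.58)² + (1.52 - 0.27)²] = 6.06 + 9.05 = +15.1

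**Width to expect for common events.** At 30% versus 45% with 66 per arm, the approximate 95% half-width is 1.96 × √[(0.30 × 0.70 + 0.45 × 0.55)/66] = 16.3 points.

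**The case against.** The strongest reply is that safety here is monitoring, not an objective. The objectives in Protocol 4 and SAP 1.0 do not mention it. Protocol 6.5.1 describes a dietary intervention without an investigational drug or product. The background does report a guideline view that programs may be prescribed "provided there is peer-reviewed published evidence of their safety and efficacy", but it then places the evidence gap in trials of efficacy. That stands: the documents do not make a safety claim the trial's purpose, which limits the weight of this point.

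A second reply is that Table 5 prints N (%) by arm, so a reader can compute any difference and interval. This is true, and it shows how little is being asked. It does not replace a pre-specified estimate.

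Three stronger readings are tempting and are not supported:
- **That the test misses a 15-point or fourfold rise more often than it finds it, whatever the rates.** At 66 per arm, power for a 15-point rise exceeds 50% at Control rates of 15% or less and of 70% or more. For a fourfold rise it is 64-73% at 4% versus 16%.
- **That non-significance will be presented as safety.** No passage says so. It is a risk that the plan leaves open, not something that it states.
- **That every row of Table 5 will probably be non-significant even if harms rise.** The calculations cover one row at a time. The joint result would need rates and correlations that the documents do not give.

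**Conclusion.** The point holds as a gap in estimation and reporting. The only inferential safety comparison is a three-arm p-value, which does not address the program-versus-Control question the trial asks and conveys no uncertainty.

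The size of the problem depends on assumed Control rates. With 66 per arm, an upper bound because Table 5 uses the mITT population, chi-square power for a 15-point rise in any AE is about 41-50% for Control rates of about 22-62%. It is 55-58% at 15% and 77-83% at 80%. For a fourfold rise in severe or serious AEs it is below 50% at Control rates up to about 2.5% (27-39% for 2% versus 8%). Fewer participants per arm lower these figures and widen the low-power range.

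No primary or secondary outcome is affected. This is an inexpensive improvement that should be made, not a flaw that undermines the trial.

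**What to change.** Keep the pre-specified chi-square or Fisher test and the N (%) columns. In SAP 11.0 and in each row of Table 5, add the TSFL-minus-Control and MEDD-minus-Control risk differences with 95% Newcombe score intervals. Add to SAP 11.0:

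> Statements about comparative safety will rest on these differences and their confidence intervals. A non-significant test will not be reported as evidence of no difference.

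Record the addition in SAP 14.0, since Protocol 8.2.3 names only the test.

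The cost is a few lines of SAP text and one table shell, with no new data. The intervals will be wide (about ±16 points for common events in the example above), so the safety statement will be less favourable than a bare non-significant p-value. The change improves estimation and interpretation. It does not increase power.

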6.5. Clinical Measurements

6.5.1. Clinic Visits

Clinic visits will include evaluations of height (Visit I only), BMI calculation (Visit I and 2 only), vital signs, prior and concomitant medication/supplement use, and inclusion/exclusion criteria (for eligibility at visit I and for potential protocol deviations at subsequent visits). In order to calculate BMI, height will be measured at the screening visit (Visit I, week -I) using a wall-mounted stadiometer. Participants will remove shoes prior to height measurement.

Standardized vital signs measurements will include resting blood pressure and heart rate measured using an automated blood pressure measurement device. Blood pressure will be obtained after the participant has been sitting for at least five min. Systolic and diastolic pressures will be measured once using an appropriate sized cuff (bladder within the cuff must encircle 2:80% of the arm). Clinic staff may take a second blood pressure and heart rate, if warranted. In the event a second measure is assessed, the second measurement will be recorded

in the eCRF. Should elevated blood pressure (see Section 6.3.2, criterion 13) be present at the screening visit (Visit 1, week -1), one retest will be allowed on a separate day, prior to Visit 2 (week 0).

Additionally, AEs will be assessed at each post-randomization visit (Visits 2, 3, 4, 5, 6, and 7; weeks 0, 2, 4, 8, 12, and 16). Inquiring about AEs will occur with an open-ended question. This study is a dietary intervention and does not include an investigational study drug or product. However, for safety purposes, assessment of AEs will be conducted in a manner consistent with clinical trials on investigational study drugs or products. Participants will be asked an open-ended question (e.g. "Have there been in any changes in your health or medications since you were last asked?").

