9.2. Adverse Event Monitoring

In a consensus view of guidelines for the design, conduct and reporting of human intervention studies to evaluate the health benefits of foods, an International Life Sciences Institute Europe Expert Group defines an AE as "any untoward medical occurrence or undesirable clinical experience in a participant in a clinical trial, whether or not considered related to the intervention" (Welch 2011). This includes any occurrence that is new in onset or aggravated in severity or frequency from the baseline condition, or abnormal results of diagnostic procedures (including laboratory test abnormalities where applicable). Therefore, clinical observations, including responses to the question, "Have there been in any changes in your health or medications since you were last asked?" will be collected post randomization. These observations will be reviewed for assessment of AE, including severity and potential relationship to the dietary intervention as determined by the study physician.

Events should be considered AEs if they:

- Result in discontinuation from the study,
- Require treatment or any other therapeutic intervention,
- Require further diagnostic evaluation (excluding a repetition of the same procedure to confirm the abnormality),
- Are associated with clinical signs or symptoms judged by the Clinical Investigator to have a significant clinical impact.

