9.2.1. Grading and Severity

The ClinicalInvestigator will evaluate all AEs with respect to their severity, and record the outcome and action taken on the AE eCRF. AEs will be graded as:

Mild:	Awareness of symptoms but easily tolerated
Moderate:	Discomfort enough to interfere with but not prevent daily activity
Severe:	Unable to perform usual activity

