9.2.2. Relationship

The Clinical Investigator will also judge the likelihood that the AE was related to the diet plan administered and document this on the appropriate eCRF as:

Jason Pharmaceuticals, Inc. BI0-1607 (MED 019) 21 .June 2016; Version 1.7 Confidential

NOT RELATED	This category applies to those adverse experiences which, after careful consideration, are clearly and incontrovertibly due to extraneous causes (disease, environment, etc.).
UNLIKELY	In general, this category can be considered applicable to those experiences that after careful medical consideration at the time they are evaluated, arc judged to be, unlikely related to the study foods administered.
POSSIBLY	This category applies to those adverse experiences for which, after careful medical consideration at the time they are evaluated, a connection with the study foods administration appears possible but cannot be ruled out with certainty.
PROBABLY	This category applies to those adverse experiences that, after careful medical consideration at the time they are evaluated, are felt with a high degree of certainty to be related to the study foods.
DEFINITELY	This category applies to those adverse experiences which, the Clinical Investigator feels are incontrovertibly related to the study foods.

Appropriate therapeutic action and follow-up measures will be performed by the Clinical Investigator in accordance with good medical practice.

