### Population(s)

	Table 1	Subject Disposition
ITT	Table 2.1	Demographic Characteristics
ITT	Table 2.2	Vitals
ITT, mITT, Completers	Table 3	Primary Outcome Variable: Body Weight (Visit 7)
ITT, mITT, Completers	Table 4.1	Secondary Outcome Variables: Body Weight (Visits 3, 4, 5, 6)
ITT, mITT, Completers	Table 4.2	Secondary Outcome Variables: Weight Loss $\geq$ 5% and $\geq$ 10%
mITT, Completers	Table 4.3	Secondary Outcome Variables: Body Composition
mITT, Completers	Table 4.4	Secondary Outcome Variables: Body Circumference Parameters
mITT, Completers	Table 4.5	Secondary Outcome Variables: hs-CRP
mITT, Completers	Table 4.6	Secondary Outcome Variable: IWQOL-Lite Questionnaire Outcomes
mITT, Completers	Table 4.7	Secondary Outcome Variable: RAND Health Survey Questionnaire Outcomes
mITT, Completers	Table 4.8.1	Secondary Outcome Variables: Satisfaction and Health/Well-being Questionnaire
mITT, Completers	Table 4.8.2	Secondary Outcome Variables: Satisfaction and Health/Well-being Questionnaire (Recoded)
mITT, Completers	Table 4.9	Secondary Outcome Variables: Program Questionnaire

mITT, Completers	Table 4.10	Secondary Outcome Variable: Weight Loss Program Adherence
mITT, Completers	Table 4.11	Secondary Outcome Variable: Nutrition Support Contact
mITT	Table 5	Summary of Subjects with at Least One Intervention-Emergent Adverse Event

**Note: Tables 3, 4.1, and 4.2 will be generated for Completers, ITT population with multiple imputation applied for the missing data and for the mITT population, both with and without imputation. For the mITT population with imputation, LOCF imputation method applied for missing data will be reflected in footnotes of relevant tables. All other tables generated for the mITT population will be without imputation.**

Table 1  
Subject Disposition

---

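### The planned adverse-event output is pooled counts only, so it cannot show which non-serious events were more frequent on TSFL or MEDD than on Control; one descriptive table by event term would close the gap

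*SAP*

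**What the plan says.** SAP 11.0 names one test on AEs: "Possible differences in the number of participants with at least one AE will be assessed with Chi-Square or Fisher's exact test". Protocol 8.2.3 has the same content and adds no breakdown by event type.

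The list in SAP 16.0 holds one AE table, Table 5, titled "Summary of Subjects with at Least One Intervention-Emergent Adverse Event" and assigned to the mITT population. Its shell in SAP 17.0 gives N (%) per arm and one intervention p-value for each of four rows: any AE, serious, severe, and related. A footnote limits the related row to events "Probably or Definitely Related to Study Treatment".

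The other planned safety outputs are:
- the row for discontinuation due to an AE in Table 1;
- vital signs by arm in Table 2.2;
- a note of participants whose BMI falls to 19.0 kg/m² or below (SAP 11.0).

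The data behind these are fuller. Protocol 9.2.5 puts every AE on its own eCRF page, Protocol 9.2.1 grades severity and Protocol 9.2.2 grades relatedness. Protocol 6.5.1 says that "assessment of AEs will be conducted in a manner consistent with clinical trials on investigational study drugs or products".

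**The concern.** Two of the three arms follow restricted plans for 16 weeks, at 800-1000 kcal/day (TSFL) and 1100-1300 kcal/day (MEDD). The natural safety question is which complaints, if any, are more common on these plans than on the self-directed diet. Serious events are reported and followed one by one (Protocol 9.2.4 and 9.2.6), so the gap lies in the non-serious ones.

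The pooled rows do not answer that question:
- The any-AE row mixes a program-specific symptom with every cold and sprain.
- The severe row leaves out mild events and also moderate ones, defined as "Discomfort enough to interfere with but not prevent daily activity".
- The related row leaves out the grade for events where "a connection with the study foods administration appears possible but cannot be ruled out with certainty". It also rests on attribution whose object varies. The investigator is told to "judge the likelihood that the AE was related to the diet plan administered", and Protocol 9.2 speaks of "potential relationship to the dietary intervention as determined by the study physician", but four of the five grade definitions refer to the study foods, which Control does not receive during the 16 weeks.

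A reader of the planned output would know how many participants had some event in each arm, but not what the events were. A flat any-AE row could then be taken as evidence that the programs carry no particular complaints.

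**Working it through.** **Is the gap real?** Three places were set side by side.

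1. SAP 11.0 and Protocol 8.2.3: participants with any AE, the low-BMI note, vital signs. Nothing by type.
2. SAP 16.0: the list runs from Table 1 to Table 5, and Table 5 is the only AE table.
3. SAP 17.0: the Table 5 shell is complete and legible, with four rows and no row by term, symptom or body system. The Table 1 row is one pooled count per arm.

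The absence therefore does not come from redaction or lost text.

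**How much does pooling dilute a specific excess?** The plan has no AE figure to reproduce, and the documents give no AE rates. What follows is an illustration on assumed rates.

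Inputs:
- Arm size: 198/3 = 66 randomised (Protocol 8.1).
- b, the background rate of participants with some other AE, the same in both arms: assumed 10%, 30%, 60%.
- p0 and p1, the rates of one symptom on Control and on a program: assumed 3% and 13%, a 10-point excess (6.6 participants of 66).

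With background AEs independent of the symptom:

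- rate in the any-AE row = 1 − (1 − b)(1 − p)
- difference between arms = (1 − b)(p1 − p0)

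| b | Control | Program | Excess shown | Participants of 66 |
|---|---|---|---|---|
| 10% | 1 − 0.9×0.97 = 12.7% | 1 − 0.9×0.87 = 21.7% | 9.0 points | 5.9 |
| 30% | 1 − 0.7×0.97 = 32.1% | 1 − 0.7×0.87 = 39.1% | 7.0 points | 4.6 |
| 60% | 1 − 0.4×0.97 = 61.2% | 1 − 0.4×0.87 = 65.2% | 4.0 points | 2.6 |

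The factor (1 − b) does not depend on p0 or p1 separately, so 0% against 10%, or 10% against 20%, gives the same excess.

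**Sensitivity to independence.** Suppose people prone to other AEs are also prone to the symptom, modelled as a latent normal correlation of 0.3 at 3% against 13%. The excess shown is then 8.1, 5.4 and 2.4 points. Independence is the milder case.

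No such figure is offered for the related row. It would need the share of cases graded probably or definitely related in each arm, and there is no basis for taking that share as equal when Control receives no study food.

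**What needs no assumed rate.** Whatever the background, no planned row names an event.

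**The case against.** The strongest reply is that little is at stake. Safety is not a stated objective in either document, no efficacy estimate is touched, and every AE is recorded. A by-type table can be produced at any time, and SAP 13.0 foresees a clinical study report in which departures from the plan are described. This stands, and it sets the level of the point. What remains is that, if the table is left to later, its inclusion and the grouping of terms would be chosen with the results in view.

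Second, dilution is a property of any pooled row, and every rate above is assumed. This also stands: the arithmetic shows the direction and possible size, not an expected loss.

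Third, the yield may be modest. AEs are elicited by one open question (Protocol 6.5.1). Protocol 9.2 says events should be considered AEs if they lead to discontinuation, treatment or further work-up, or have a significant clinical impact in the investigator's judgement. Many mild diet symptoms may never reach the AE page, and a table by term would not show them either. RAND-36 energy/fatigue and pain scores (Table 4.7) touch two symptoms, but as scores and not as AEs.

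Two stronger readings are tempting. A reader might infer that the plan hides or discards harm data. The documents do not support that: AEs are recorded, serious ones are followed individually, and nothing forbids a further table or listing. SAP 16.0 enumerates tables only, so the lack of a named listing is weak evidence on its own. A reader might also hold the plan in breach of its drug-trial standard in Protocol 6.5.1, but that sentence concerns how AEs are assessed, not how they are tabulated.

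**Conclusion.** The point holds as a cheap improvement of minor severity. All planned AE output consists of pooled counts by arm: the four rows of Table 5 and one row of Table 1. Vital signs and the low-BMI note do not identify the type of AE. The plan therefore cannot show which non-serious events were more frequent on TSFL or MEDD than on Control.

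That conclusion rests on the table list and shells alone. The dilution factor of 0.9 to 0.4 rests on assumed background rates of 10% to 60% and on independence. No power claim is made, because the remedy is descriptive. This is a gap in reporting, not a loss of data.

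**What to change.** In SAP 11.0 and 16.0, with a shell in 17.0, add a descriptive Table 5.1:
- Population: all randomised participants (ITT). Table 5 uses mITT, which leaves out AEs in anyone without a post-baseline weight.
- Content: N (%) of participants with one or more intervention-emergent AEs, by reported term within body system, by arm and maximum severity, whatever the relatedness grade.
- Grouping: assign terms to body systems from a listing without the arm column. Neither document names a coding dictionary, so the SAP should state the grouping rule.
- No p-values.

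Keep Table 5 as the overall summary, and add a sentence to SAP 11.0 that a non-significant any-AE test is not read as no difference in specific events.

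The cost is SAP wording, one shell and the work of grouping terms already on the eCRF, with no new data, visits or participants. The downside is sparse rows in which chance imbalances will appear, which is why the table carries no tests. Symptoms below the Protocol 9.2 threshold will still be missing.
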